2 OBJECTIVES

2.1 Pilot trial Primary Objectives

- 1. Specific Aim 1: Does nutritional supplementation facilitate cognitive function in adult breast cancer survivors, relative to persons who do not receive this supplementation?** We predict that adult breast cancer survivors receiving nutritional supplementation will experience improved cognitive performance as assessed by a battery of standardized tests of cognitive function. The current pilot study will evaluate the feasibility of administration of the nutritional supplement and placebo in this patient population and performing cognitive function testing at baseline and post supplementation.

2. **Specific Aim 2: Is the facilitation of cognitive function in the nutritional supplementation group mediated by changes in markers of oxidative stress and inflammation, relevant to cognitive performance?** We predict that persons receiving nutritional supplementation will exhibit larger changes in antioxidant markers and that these changes will serve to mediate or explain differences in the cognitive performance of the two groups. The current pilot study will evaluate the feasibility of administration of the nutritional supplement and placebo in this patient population and testing antioxidant levels at baseline and after the supplementation.

3. **Specific Aim 3: Does nutritional supplementation facilitate cognitive function in adult breast cancer survivors, relative to persons who do not receive this supplementation as indicated by changes in structural and resting-state functional markers observed utilizing the MRI/fMRI?** We predict that adult breast cancer survivors receiving nutritional supplementation will experience improved cognitive performance as assessed by a battery of structural and functional changes in imaging markers in the brain. The current pilot study will evaluate the feasibility of administration of the nutritional supplement and placebo in this patient population and performe structural and resting-state functional MRI to evaluate changes in these imaging markers at baseline and after the supplementation.

3.0 SUMMARY OF STUDY PLAN

[figure not shown]
This pilot project is a randomized clinical trial of the feasibility of administering the nutritional supplement and placebo, performing a battery of cognitive function testing, structural and resting-state functional MRIs, and antioxidant levels at baseline and post supplementation in a target group of breast cancer survivors treated with chemotherapy. Prior to study initiation, the Human Subjects Committee will approve all study procedures. This goal of this pilot feasibility study is to provide a comprehensive assessment of a clinical trial's specific challenges as well as strategies to mitigate risks before a well- powered clinical trial can be proposed and implemented.

Research teams that use feasibility studies experience faster clinical trial accrual and significantly fewer delays in enrollment than those that forgo this preliminary assessment. A properly conducted clinical trial feasibility study can provide information regarding:

- Biomarker methodologies/estimations
- Effect size estimations
- Compatibility of the clinical trial treatments and assessments with current patterns of care
- Available patient population
- Likelihood of patients agreeing to participate in the clinical trial
- Potential modifications to clinical trial design and eligibility criteria to enhance enrollment
- Competing clinical trials
- Site capabilities
- Research infrastructure
- Personnel
- Equipment
- Regulatory requirements and timelines
- Local institutional review board/independent ethics committee (IRB/IEC) review timelines
- Investigator grant requirements and site contracts
- Projected patient enrollment rates.

The current feasibility pilot trial is to inform the research team of all these above challenges that occur with clinical trials and can contribute to the proposal and conduct of a well powered clinical trial.

Nutritional Supplementation (COGNUTRIN®) in Breast cancer Patients with Cognitive Impairment: Study Schema

4.0 PARTICIPANT SELECTION

Women who have been diagnosed with stage I-III B breast cancer (BCa) and who have completed neoadjuvant or adjuvant treatment with anthracyclines and/or taxanes + or – Radiation therapy within the past 6 months (+/- 7 days) will be invited to be screened for eligibility to participate in this trial (subjects on concurrent endocrine therapy (TAM, Aromatase inhibitors are also eligible to participate as this is standard of care for this patient population). We will, in addition, expand our recruitment at the Moffitt Cancer Center to include the members of the Moffitt Cancer Center Affiliate Network (Total Cancer Care network consisting of 16 community hospital affiliates and 415 community oncologists statewide. With this additional network to recruit this patient population from, we are confident that we will be able to recruit the number of subjects needed for this study from each site. Based on the number of subjects that can be recruited from Moffitt, we conservatively estimate that we will recruit and retain 40 subjects during the 6 months recruitment period. Throughout the recruitment, data collection and retention period of this study we will focus on retaining high participation rates of an ethnically diverse population.

If women are already patients at Moffitt Cancer Center or one of its affiliates, they will be identified by one of the medical oncologists who are co-investigators in this trial based on the diagnosis and treatment received. Women who have been diagnosed with stage I-IIIB breast cancer (BCa) and who have completed neoadjuvant or adjuvant treatment with anthracyclines and/or taxanes + or – Radiation therapy within the past 6 months, (+/- 7 days) will be referred to the clinical research coordinator who will then invite these potentially eligible subjects to be screened for eligibility criteria to participate in this trial. All subjects referred to the research team from affiliate sites will be screened for eligibility. In this pilot clinical trial, all subjects, if identified as eligible based on initial screening in any other site other than the Moffitt Cancer center, will be required to come to the Moffitt cancer center if willing to continue to participate.

Although cognitive complaints are reported frequently after breast cancer treatments, their association with standardized neuropsychological (NP) test performance is not well-established. The lack of association between NP test performance and subjective cognitive complaints in prior studies with breast cancer patients^{156-157,160} could reflect the lack of specificity and sensitivity of the self-report tools, or could be due to reliance on global measures rather than domain-specific assessments. There is also a skepticism regarding the validity of cognitive complaints and their relationship to NP test performance in cancer patients. A few more recent studies have suggested that patient self-report is associated with relevant domains of NP function, which is strongest for memory complaints. There is an emerging literature supporting the ability of individuals to subjectively detect changes in cognitive function that precedes statistically significant changes in NP performance or structural imaging abnormalities¹⁵⁸. There is thus significant support for the value of patient-reported outcomes as a central measurement in evaluation of cancer treatment-related morbidities¹⁵⁹, including domains of cognitive impairment.

Therefore, based on the current body of research, the inclusion criteria in this trial will be based on subjective cognitive complaints in cancer survivors. Inclusion criteria to identify women who met the inclusion criterion for chemotherapy-induced cognitive impairment, we will use the most current approach described by Ferguson et al (2012)¹⁶⁰ where each subject will be required to answer in the affirmative: ‘do you have problems with memory and attention since having chemotherapy, and do you believe chemotherapy contributed to the problems?’

4.1 Inclusion Criteria. 1) Women 30-70 years of age 2) Cases with Stage I-IIIB Breast Cancer that have completed neoadjuvant or adjuvant treatment with anthracyclines and/or taxanes + or –Radiation therapy within past 6 months (+/- 7 days) (subjects on concurrent endocrine therapy (TAM, Aromatase inhibitors are also eligible to participate as this is standard of care for this patient population) 3) Able to understand and sign the informed consent. 4) Fluent in reading, comprehension and communication in the English language. (Persons who are unable to meet this requirement are excluded from the current proposal because many of the cognitive tests that are administered are in English and translation of these instruments in other languages is currently unavailable) 5) No evidence of dementia (MMSE \geq 23) but some evidence of cognitive impairment (each subject will be required to answer in the affirmative: ‘do you have problems with memory and attention since having chemotherapy, and do you believe chemotherapy contributed to the problems?’); 6) Each subject must be aware of the nature of his current medical condition and must be willing to give consent after being informed of the experimental nature of therapy, alternatives, potential benefits, side-effects, risks and discomforts. 7) ECOG performance status of 0- 2 (8) Acceptable hemoglobin and hematocrit level based on CBC. (9) All subjects must be willing to be monitored for adequacy of nutritional intake during the intervention, as is the current standard of clinical practice.

4.2 Criteria for exclusion will include: 1) Use of estrogens (oral, dermal or vaginal), progesterone (oral or topical), or androgens during the previous 3 months, 2) Use of over the counter steroid hormonal supplements 3) Patients with advanced or Stage IIIC or IV breast cancer or other cancers. 4) Use of n-3 fatty acids or high dose antioxidant supplements other than what is provided in the trial. 5) History of known allergy to components of the study supplements. 6) Subjects with renal or liver disease (AST/ALT $>$ 5.0 x upper limit of normal as evidenced by impairment of baseline laboratory values); Actual creatinine clearance of $<$ 60 utilizing the Cockcroft-Gault formula (1976), which employs creatinine measurements and a patient's weight to predict the clearance. (The constant for women is 1.04). 7) Concurrent participation in another chemoprevention trial. 8) Evidence of bleeding diathesis or coagulopathy (PTT and/or either PT or INR $>$ 1.5x upper limit of normal (except for subjects receiving anti-coagulation therapy). Concurrent use of Coumadin or Warfarin will be acceptable and monitoring patients on warfarin or Coumadin will follow the standard of care as dictated by the prescribing physician (PT/PTT). If the prescribing physician is not a Moffitt MD, then the prescribing MD

will be notified by the research staff of the subject participating in the study, and monitors for PT, PTT will be obtained from patient during the 3 month study visit for review. 9) Subjects with metabolic abnormalities (e.g. thyroid disorders, insulin dependent diabetes, rheumatologic disease etc.). Subjects with metabolic disorders (a) who are otherwise eligible, (b) treated for hypothyroidism by their primary MD with Synthroid (levothyroxine) and (c) with the approval of the Moffitt treating oncologist will not be excluded from the study. 10) Patients with known claustrophobia, presence of pacemaker and/or ferromagnetic material in their body that would prohibit MRI imaging (ex. tissue expanders). 11) Medical history of concussions 12) Other acute or chronic medical or psychiatric condition or laboratory abnormality that may increase risk associated with study participation or study drug administration, or may interfere with interpretation of study results, and in the judgment of the investigator would make the subject inappropriate for entry into this study.

Our criteria for inclusion of subjects in this trial is that subjects recruited are able to understand and sign the informed consent. The subjects must also be fluent English-speaking (Persons who are not fluent English speakers are excluded from the current proposal because many of the cognitive tests that are administered are language-based and are heavily influenced by first language). Subjects must also have no evidence of dementia (MMSE \geq 23) but some evidence of cognitive impairment (each subject will be required to answer in the affirmative: ‘do you have problems with memory and attention since having chemotherapy, and do you believe chemotherapy contributed to the problems?’). Each subject must be aware of the nature of his current medical condition and must be willing to give consent after being informed of the experimental nature of therapy, alternatives, potential benefits, side-effects, risks and discomforts. If a subject is determined to be cognitively impaired to the point of not meeting the above criteria at screening by the investigative team, they will not be included in this pilot phase of the clinical trial, making the use of proxy’s unnecessary.

4.3 Anticipated problems with subject recruitment and retention: Our group has extensive experience conducting research with breast cancer patients as well as studies collecting neuropsychological data, questionnaires, blood samples, and MRI/fMRI. Thus, we expect difficulties to be minimal. As with all clinical trials, we anticipate that there will a 10% loss of subjects to follow up, although, in our experience, breast cancer survivors tend to be a highly motivated group and the time between assessments is short and subjects will be required to come in monthly for monitoring safety and compliance. Moffitt Cancer center, as the only NCI designated Comprehensive cancer center in the State of Florida has a substantial number of subjects treated for breast cancer.

The recruitment, intervention and retention team (PI, [name], Co-I [name] and CRC) will initiate, develop and implement procedures to deal with and solve problems with attrition. As we have with our previous and current intervention trials, we will take measures to ensure that loss to follow-up is minimal, implementing several strategies for recruitment and retention as follows:

- a. Contact with participants will be maintained by their preferred method or methods: phone numbers, primary and secondary mailing addresses, and e-mail addresses updated at each contact.
- b. At each visit, current contact information will be verified and an alternate means of contacting the person will be established with the permission of the participant. For example, friends, family members, and summer addresses will be maintained with the consent of the participant.
- c. Reminder calls and/or e-mails the day prior to the appointment.
- d. Monetary compensation for travel: Because of the importance of retaining participants for the duration of the study, participants will be provided \$50 for each visit to cover travel expenses. Participants traveling more than 100 miles from their home to reach the research site will receive an additional \$30 for transportation costs.
- e. Empathetic, warm and experienced clinical research coordinators and study staff who can establish rapport with participants.
- f. Telephone contact will be encouraged with calls from the research staff to the subject at least once a month between visits.
- g. Appointments will be made at the participants’ convenience including evenings or early mornings.
- h. Monthly and follow up visits will occur in the comfort of the Breast Program clinics to ensure familiarity of staff and environment.
- i. Valet parking for all subjects, free of charge.

- j. Weekly staff meetings will occur and case studies will be reviewed to observe patterns and etiology of attrition of participants will be discussed.

5.0 PHARMACEUTICAL INFORMATION:

5.1 COGNUTRIN: The choice of the supplement to use in this trial is based on relevant research supporting the various components as well as the use of a commercially available dietary supplement. The supplement to be used will be a combination of 2 standardized formulations (a) antioxidants from blueberry extracts - VitaBlue™ (40% polyphenolics, 12.5% anthocyanins from blueberries (BB) and (b) omega 3-fatty acids - Lovaza®. The standardized agent - Lovaza is manufactured by Glaxo Smith Kline and will be purchased for use in this study. However, the blue berry anthocyanins was purchased from a standard manufacturer and encapsulated at the dose for this specific study using FDA standards in a certified formulary and tested by an independent laboratory for composition (FDA IND 116424). The matching placebos were also manufactured for this study using FDA standards- all of which have been evaluated and approved for use by the FDA. As indicated in the protocol, these are 2 separate products administered separately (pages 8-11). The combination that will be used has met the standards of the FDA and an IND has been approved by the FDA (FDA IND 116424) for use of this agent combination in this study. Our team took into consideration the high patient burden to the subjects due to large size if the agents were combined into one capsule and thus decided to keep them as 2 separate agents.

The supplement COGNUTRIN is a term coined by the PI to denote the combination of 2 standardized formulations (a) VitaBlue™ (40% polyphenolics, 12.5% anthocyanins from blueberries (BB) and (b) n-3 fatty acids- Lovaza®. We have obtained IND (FDA IND 116424) from the FDA for this current indication proposed from the FDA. We have not submitted a patent for this product but hope to explore the potential to license this combination if successful in the future. We are currently working on obtaining a registered trademark with this name that we coined –COGNUTRIN. Our goal is to develop this combination agent scientifically, maintain exclusivity and to not be confused with myriads of supplements in the market place.

5.1.1 VitaBlue™ (BB Anthocyanins): VitaBlue™ is a freeze dried high potency extract from blueberries. VitaBlue™ is created using a unique proprietary process from VDF FutureCeuticals. It comes as a standardized powder containing blueberry anthocyanins that is ready for encapsulation.

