6.5 Dose and Toxicity Management: We will ensure that our protocol and informed consent comply with FDA recommendations. In addition, we have planned monthly visits to monitor daily symptoms monitor and will perform an interview for adverse events, unusual symptoms, change in medical condition and concomitant medications use. Any abnormality observed will be communicated by the research coordinator to the study MD for evaluation and for continuation in the study. Subjects in the study will be dropped from study until which time the symptom is determined to be unrelated to the study agent as determined by the study MD. We will provide each subject with a 24- hour contact phone number and specific instruction on contacting the research team including the MD in this study. In addition, evaluation of safety in this subject population has been added as a specific aim of the trial with a formal comparison of safety between active and placebo arms, further illustrating our commitment to ensuring subject safety in this and future clinical trials.

A patient's treatment will be discontinued in any of the following circumstances: (a) Allergic reaction to product; (b) Dramatic change in stool frequency; (c) Start of other treatments that may cause malabsorption; (d) Request of patient of MD or patient; (e) Unusual symptoms reported during follow-up or other unusual symptoms or blood work results observed during the study period; and, (f) Persistent nausea not controlled with antiemetics. There are no reductions in the Cognutrin® dose. If adverse events occur that require holding Cognutrin ® (until etiology is determined), the dose will remain the same once treatment resumes. Any toxicities associated or possibly associated with Cognutrin ® treatment will be managed according to standard medical practice. Subjects will be assessed clinically for toxicity prior to, during intervention on a monthly basis and at end of intervention. If >grade III toxicity occurs because of Cognutrin ® at any time during the study, treatment with Cognutrin ® will be discontinued. We will also inquire about hypersensitivity to fish/and or shellfish and symptoms of atrial fibrillation at each visit. All subjects will be followed by their medical oncologists for their cancer treatment, using the routine surveillance guidelines as established by the Cancer Center during the study.

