Adverse events requiring delays or permanent discontinuation of Cognutrin® are listed in the table below:

Event	Action
Grade 1 & 2 constitutional, dermatological, gastrointestinal (GI), metabolic and pain symptoms Examples: Rash Allergic rhinitis, cough, bronchitis. Abdominal Pain Belching/Gas Nausea/Vomiting Diarrhea	No Action Required Inform MD Document event in research and medical record
Grade 3	Discontinue Cognutrin ®/Notify Study PI
Grade 4	Discontinue Cognutrin ®/Notify Study PI
Grade 2, 3, or 4 abnormal liver function tests ^{1,2} as determined by NCI CTC version 4.0	Discontinue Cognutrin ®/Notify Study PI and Monitor until it returns to normal

1. Tests used to monitor liver function include: albumin, total and direct bilirubin, alkaline phosphatase, AST, ALT, total protein, PT/PTT.)
2. In the event that PT/PTT is abnormal due to anticoagulant therapy, treatment and/or drug discontinuation will be at the discretion of the site investigator/MD.

Regardless of the reason for holding study drug treatment, the maximum allowable length of treatment interruption is 1 week. Interruption of intake of >1 week will result in discontinuance of subject from the study. Patients who have an ongoing Cognutrin ®-related Grade 3-4 or serious adverse event at the time of discontinuation from study treatment will continue to be followed until resolution of the event or until the event is considered irreversible by the study MDs.

In addition, a standard multivitamin/ mineral preparation will be provided free of charge during the study duration, to assure a consistent baseline intake of essential vitamins and minerals among all study participants during the study period and to encourage subjects from not using other supplements that may contain components of the study agents. Subjects in the treatment and placebo arms will be provided these multivitamin/mineral supplements and instructed to consume 1 tablet daily with the dinner meal.

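### Section 4.2 item 6 sets a numeric liver limit at entry only for AST/ALT, while the Section 6.5 table stops agent for any Grade 2 to 4 liver test, so dosing can start at a value listed for stopping

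*Combined protocol and SAP*

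**What the plan says.** **Entry.** Section 4.2 item 6 excludes renal or liver disease. Its hepatic number is AST or ALT above "5.0 x upper limit of normal as evidenced by impairment of baseline laboratory values"; its other number is a creatinine clearance. Sections 4.1 and 4.2 give no figure for bilirubin, alkaline phosphatase, albumin or total protein. Item 8 excludes PTT, PT or INR above 1.5 x ULN, except in women on anticoagulants. Item 12 lets the investigator exclude for a laboratory abnormality on judgment, without a number.

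**Stopping.** The Section 6.5 table is introduced as "Adverse events requiring delays or permanent discontinuation of Cognutrin". One row reads "Grade 2, 3, or 4 abnormal liver function tests", graded by NCI CTC version 4.0. Its action is to discontinue agent, notify the PI and monitor until normal. Footnote 1 defines the tests: "Tests used to monitor liver function include: albumin, total and direct bilirubin, alkaline phosphatase, AST, ALT, total protein, PT/PTT". Footnote 2 gives the one exception, for PT/PTT that is abnormal because of anticoagulants.

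**Surrounding text in Section 6.5.** The general toxicity rule carries an attribution condition: "grade III toxicity occurs because of Cognutrin". Discontinuation item (e) covers "other unusual symptoms or blood work results observed during the study period". A hold is foreseen: "until etiology is determined), the dose will remain the same once treatment resumes". Holds are limited: "Regardless of the reason for holding study drug treatment, the maximum allowable length of treatment interruption is 1 week". Any abnormality goes to the study physician, who evaluates it and decides on continuation.

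**Timing.** Chemistry is obtained at screening or taken from the previous 28 days (Section 7.1, Table 1, note 4). It is repeated at weeks 4 and 8 (Section 7.4.2.3) and at week 12.

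**The concern.** A value that the protocol says should end dosing does not, by any number, prevent dosing from starting. That is first a matter of participant protection. The first scheduled on-treatment chemistry is at week 4, so a woman could take agent for about 3 to 5 weeks before the mismatch comes up.

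The second matter is exposure. If the row is applied literally at week 4 to a value that has not changed since screening, she loses most of her planned treatment for a reason unrelated to the agent. Such a stop would also count in the tolerability experience that this pilot is meant to pass on to a larger trial.

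**Working it through.** No published figure has to be reproduced. The check compares, test by test, the values allowed at entry with the values listed for stopping.

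| Test (6.5, footnote 1) | Passes the numeric entry rule | Listed for stopping | Overlap |
|---|---|---|---|
| Total and direct bilirubin, alkaline phosphatase, albumin, total protein | No numeric limit | Grade 2 to 4 | Any gradable value at Grade 2 or above, wherever the cut-points lie |
| AST, ALT | Up to 5.0 x ULN | Grade 2 to 4 | From b to 5.0 x ULN, where b is the lower bound of Grade 2 |
| PT/PTT | Up to 1.5 x ULN; women on anticoagulants exempt (item 8) | Grade 2 to 4; discretionary on anticoagulants (footnote 2) | No clear conflict |

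**AST/ALT overlap.** The documents do not print b, so it is an assumption. Width = 5.0 - b. For b = 2.5, 3.0, 4.0 and 5.0 x ULN the width is 2.5, 2.0, 1.0 and 0 x ULN. The first row of the table needs no such figure.

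**Exposure lost if a woman is stopped** (12 planned weeks, visits +/- 7 days):
- Week 4: (12 - 4)/12 = 67%. With the window, (12 - 5)/12 = 58% to (12 - 3)/12 = 75%.
- Week 8: (12 - 8)/12 = 33%. With the window, 3/12 = 25% to 5/12 = 42%.
- Held, then cleared within the 1-week cap: at most 1/12 = 8%.
- Share of the active arm: 20 x 12 = 240 woman-weeks, so one woman stopped at week 4 removes 8/240 = 3.3%.

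**How many women.** The documents give no prevalence of Grade 2 or higher liver tests in this population. I assume 0.5% to 2%.
- Expected number with a qualifying value: 40 x 0.005 = 0.2 to 40 x 0.02 = 0.8.
- Chance of at least one: 1 - 0.995^40 = 18% to 1 - 0.98^40 = 55%.
- The expected number reaches one only at a prevalence of 1/40 = 2.5%.
- About half would be on placebo, so 0.1 to 0.4 are expected in the active arm. If every one of them stopped at week 4, the arm would lose 0.1 x 8/240 = 0.3% to 0.4 x 8/240 = 1.3% of its exposure.

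These counts are of women with a qualifying value, not of women stopped. A stop also requires that item 12 was not used, that the value persists, and that the study physician does not clear her.

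**The case against.** The strongest reply is that the protocol already has a route for an unchanged value. Section 6.5 sends any abnormality to the study physician for a decision on continuation, and suspends the woman only until the finding is judged unrelated. The screening chemistry is on file, so the comparison fits within the 1-week cap. Section 10.1.4 presumes drug causation except where an event is clearly unrelated, and a value that predates the first dose is a good candidate for that exception. The table is headed as adverse events and its heading mentions delays. The row's monitoring to normal suggests an on-study change. Section 7.7.8 catalogues screening findings as baseline symptoms. A stopping limit stricter than the entry limit can also be a deliberate, cautious choice.

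Much of this stands. A reader might infer that a woman with a Grade 2 baseline value must be stopped at week 4; the documents do not support that, because physician review may spare her. A reader might also infer that different sites would treat the same value differently. Section 4.0 brings every participant to one center, so that argument has no footing.

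What the reply does not supply is an entry limit or a baseline condition in the row. Item 12 is discretionary. The adverse-event start point is not uniform: Section 10.1.1 uses the start of agent, while Sections 8.1 and 12.6 use consent. These are recording and evaluation windows rather than stopping rules, but they leave the status of a baseline finding unsettled. The drafters did write matching entry and stopping exceptions for PT/PTT, and wrote attribution into the general toxicity rule. The other liver tests received neither.

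**Conclusion.** The mismatch holds on the text. For bilirubin, alkaline phosphatase and albumin it needs no outside figure; for AST/ALT it rests on Grade 2 beginning below 5.0 x ULN. PT/PTT is not part of the problem.

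Its size is small. The number affected is probably under one woman of 40, which depends on the assumed prevalence of 0.5% to 2%. The loss of exposure is conditional on persistence and on the physician's decision.

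A reader might infer harm to the efficacy or between-arm results, and the documents do not support that either. Section 8.4 still calls for the post-intervention procedures as far as possible, Section 12.7 assesses every participant for response, and randomization should spread baseline abnormalities across the arms. This is a minor alignment of a safety rule, worth making because it is cheap.

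**What to change.** In Section 4.2 item 6, exclude women whose screening AST, ALT, total or direct bilirubin, alkaline phosphatase or albumin, where reported and gradable, is already Grade 2 or higher by CTC version 4.0. The documents do not show whether total protein has a grade; if it does, add it.

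The cost is one sentence and no new test, since the chemistry panel is already required. The downside is a few lost candidates, including some whose values would have improved: under 1 per 40 at the assumed prevalence. That deserves some weight, because the May 2014 amendment letter reports over 90 women screened in 30 days with none eligible under the criteria then in force.

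Alternatively, if the study physicians accept dosing at such values, word the Section 6.5 liver row as applying to results that are new or worsened from baseline. That loses no candidates. Either change makes the decision explicit.
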